11.6 Return Product Analysis

Study Sponsor representatives and their contact information are provided in the MOP that accompanies this protocol.

Recoverable Alcon Products associated with device deficiencies and/or product related AEs should be returned to the Sponsor with the appropriate return forms.

11.7 Unmasking of the Study Treatment

Not applicable; this study is open-label, unmasked study.

11.8 Follow-Up of Subjects with Adverse Events

The Investigator is responsible for adequate and safe medical care of subjects during the study and for ensuring that appropriate medical care and relevant follow-up procedures are maintained after the study.

The Investigator must provide the Study Sponsor with any new safety information (which includes new AEs and changes to previously reported AEs) that may affect the safety evaluation of the device. For AEs that are unresolved/ongoing at time of subject exit from study, any additional information received at follow-up should be documented in the eCRFs up to study completion (ie, database lock).

All complaints received after this time period will be considered and processed as spontaneous (following the postmarket vigilance procedures) and should be communicated to the medical device's manufacturer as per local requirements.

11.9 Pregnancy in the Clinical Study

Pregnancy is not reportable as an AE; however, complications may be reportable and will be decided on a case-by-case basis. An Alcon form will be utilized to capture all pregnancy-related information until birth of the child.

12 ANALYSIS PLAN

12.1 Subject Evaluability

Subject evaluability will be determined prior to the [REDACTED] final database lock, based upon the Deviations and Evaluability Plan (DEP).

12.2 Analysis Sets

The Safety Analysis Set (SS) will include all eyes with attempted IOL implantation (successful or aborted after contact with the eye). The SS will be the primary set for all safety analyses.

All-Implanted Analysis Set (AAS) includes all eyes with successful IOL implantation with at least one post-operative visit and will be the primary analysis set for all effectiveness analyses [REDACTED]

[REDACTED]

- [REDACTED]
- [REDACTED]
- [REDACTED]

[REDACTED]

12.3 Demographic and Baseline Characteristics

Demographics and baseline characteristics will be summarized by IOL model (TFNT30 vs TFNT40/TFNT50/TFNT60) and all models combined using descriptive statistics based on the type of variable for AAS and SS. Demographics include age, sex, race and nationality. Baseline characteristics include BCDVA, axial length, anterior chamber depth, keratometry, corneal astigmatism. [REDACTED]

[REDACTED]

For categorical variables, number and percentage of eyes/subjects in each category for non-missing data will be presented such as sex, age group (< 65 years; ≥ 65 years), and race. For continuous variables, the number of non-missing eyes/subjects, mean, standard deviation, median, minimum, and maximum values will be presented.

12.4 Effectiveness Analyses

This is a single arm descriptive study. No formal statistical hypothesis testing is planned for any endpoint, rather, the data will be summarized using descriptive statistics.

Binocular endpoints will be summarized at the subject level [REDACTED]

12.4.1 Analysis of Key Effectiveness Endpoint(s)

All effectiveness endpoints will be summarized for each visit with Month 3 and 6 visit results being the key endpoint.

- Mean monocular residual manifest cylinder for all operative eyes for all IOL models combined
- Percent of IOLs with < 10 degree rotation for all operative eyes (rotation defined as the difference in IOL axis of orientation from postop day 1)
- Mean binocular BCDVA at 4m in photopic lighting condition
- Mean binocular DCIVA at 60cm in photopic lighting condition
- Mean binocular DCNVA at 40 cm in photopic lighting condition

12.4.1.1 Statistical Hypotheses

No hypothesis testing of the key effectiveness endpoints is planned.

12.4.1.2 Analysis Methods

Monocular residual manifest cylinder will be summarized by visits by IOL model (TFNT30 vs TFNT40/TFNT50/TFNT60) and all models combined for first eye and second eye and all eyes combined with descriptive statistics (the number of observations, mean, median, standard deviation, minimum, maximum, and two-sided 95% CI of the mean).

IOL rotation will be summarized by sample size, number, percent, and cumulative percent for the following categories of absolute rotation: (< 10 and < 20 degrees) for all models combined.

Binocular photopic BCDVA, DCIVA and DCNVA will be summarized by visits with descriptive statistics.

[Redacted]

[Redacted]

- [Redacted]

- [Redacted]

- [Redacted]

- [Redacted]

- [Redacted]

- [Redacted]

- [Redacted]

- [Redacted]

- [Redacted]

- [Redacted]

- [Redacted]

[Redacted]

[Redacted]

[Redacted]

[Redacted]

[Redacted]

[Redacted]

[REDACTED]

12.5 Handling of Missing Data

No missing data will be imputed.

12.6 Safety Analyses

There are no safety hypotheses planned in this study. The focus of the safety analysis will be a comprehensive descriptive assessment of occurrence of adverse events as well as the other listed parameters. Descriptive statistics will be provided by all model combined for first and second eyes that undergo attempted implantation.

12.6.1 Analysis of Key Safety Endpoint(s)

The key safety endpoints are:

- Rate of SSIs (including rate of SSIs related to optical properties of the IOL and rate of all SSIs)
- Rates of severe and most bothersome (separately) visual disturbances reported by QUVID questionnaire for subjects with binocular implantation by visit
- Rates of adverse events

12.6.1.1 Statistical Hypotheses

No hypothesis testing of the key safety endpoints is planned.

12.6.1.2 Analysis Methods

Rate of SSIs for either eye will be summarized by operative eye.

Descriptive summaries (counts and percentages) for rates of severe and most bothersome (separately) visual disturbances as reported by the subjects using the QUID questionnaire will be presented. These rates are accompanied by two-sided 95% CIs.

All AEs will be coded using the Medical Dictionary for Regulatory Activities (MedDRA). Ocular AEs will be summarized by operative eye. Descriptive tables (count and percentage) and listing will be generated for AEs based upon the categories of ocular and monocular AEs, serious and non-serious AEs, as appropriate.

[Redacted]

- [Redacted]
- [Redacted]
- [Redacted]
- [Redacted]
- [Redacted]
- [Redacted]
- [Redacted]
- [Redacted]

[Redacted]

[Redacted]

[Redacted]

[Redacted]

[Redacted]

[Redacted]

[Redacted]

[REDACTED]

[REDACTED]

[REDACTED]

[REDACTED]

[REDACTED]

[REDACTED]

12.8 Sample Size Justification

The choice of sample size is not based on statistical considerations.

Approximately 56 subjects will be bilaterally implanted to obtain data for at least 50 subjects (100 eyes) at Month 6, assuming a dropout rate of 10% over a 6 month period. The precision estimates below are presented for individual eye summaries. All eye summaries will have increased precision.

For visual acuity, with a sample size of 50 eyes and assuming a standard deviation of 0.18 logMAR [REDACTED] a two-sided

95% confidence interval based on large sample z statistics will extend 0.05 logMAR from the observed mean.

For residual cylinder, a two-sided 95% confidence interval based on large sample z statistics will extend 0.11 D from the observed mean, assuming a standard deviation of 0.40 D [REDACTED]

For any event where a zero incidence is observed in 50 eyes implanted with study IOL, the upper exact binomial 95% confidence limit is less than 6%. Thus, with 95% confidence, the true adverse event rate is less than 6%.

13 DATA HANDLING AND ADMINISTRATIVE REQUIREMENTS

13.1 Subject Confidentiality

The Investigator must ensure that the subject's anonymity is maintained throughout the course of the study. In particular, the Investigator must keep an enrollment log with confidential identifying information that corresponds to the subject numbers and initials of each study participant. At the end of the clinical study, the Study Sponsor will collect a copy of the enrollment log *without any identifying subject information*. All documents submitted to the Study Sponsor will identify the subjects exclusively by number and demographic information. No other personally identifying information will be transmitted to the Study Sponsor.

The Study Sponsor may release anonymized study data to external researchers for purposes of future research directly related to the study objectives, or future research that is beyond the scope of the current study objectives. The Informed Consent Form explains this to study subjects. Anonymization means that all identifiable information will be removed from the dataset and all links to the subjects in the study will be removed. Anonymization of the data will maintain confidentiality of the subjects who participate in the study so that they cannot be identified by external researchers. The anonymized data set will contain records from all of the subjects in the current study, but the anonymization process might change the data set in some ways, so external researchers will be informed that they might not be able to duplicate some of the results from this study.

13.2 Completion of Source Documents and Case Report Forms

The nature and location of all source documents will be identified to ensure that original data required to complete the CRFs exist and are accessible for verification by the site monitor,

and all discrepancies shall be appropriately documented via the query resolution process. Site monitors are appointed by the Study Sponsor and are independent of study site staff.

If electronic records are maintained, the method of verification must be determined in advance of starting the study.

At a minimum, source documents include the following information for each subject:

- Subject identification (name, sex, race/nationality)
- Documentation of subject eligibility
- Date of informed consent
- Dates of visits
- Documentation that protocol specific procedures were performed
- Results of study parameters, as required by the protocol
- IP accountability records
- Documentation of AEs and other safety parameters (if applicable)
- Records regarding medical histories and the use of concomitant therapies prior to and during the study
- Date of study completion and reason for early discontinuation, if applicable

It is required that the author of an entry in the source documents be identifiable. Direct access to source documentation (medical records) must be allowed for the purpose of verifying that the data recorded on the CRF are consistent with the original source data.

Only designated individuals at the site will complete the CRFs. The CRFs must be completed at regular intervals following the clinical study visit schedule. It is expected that all data reported have corresponding entries in the source documents. The Principal Investigator is responsible for reviewing and certifying that the CRFs are accurate and complete. The only subject identifiers recorded on the CRFs will be subject number, and subject demographic information.

13.3 Data Review and Clarifications

A review of CRF data to the subject's source data will be completed by the site monitor to ensure completeness and accuracy. After the CRFs have been completed, additional data clarifications and/or additions may be needed as a result of the data cleaning process. Data clarifications are documented and are part of each subject's CRF.

13.4 Sponsor and Monitoring Responsibilities

The Study Sponsor will designate a monitor to conduct the appropriate site visits at the appropriate intervals according to the study monitoring plan. The clinical investigation will be monitored to ensure that the rights and well-being of the subjects are protected, the reported data are accurate, complete, and verifiable from the source documents, and the study is conducted in compliance with the current approved protocol (and amendments[s], if applicable), with current GCP, and with applicable regulatory requirements.

The site may not screen subjects or perform the informed consent process on any subject until it receives a notification from an appropriate Study Sponsor representative that the site may commence conducting study activities. Monitoring will be conducted periodically while the clinical study is ongoing. Monitoring methods may include site visits, telephone, written and fax correspondence. Close-out visits will take place after the last visit of the last subject at the site.

A Coordinating Investigator may be identified by the Study Sponsor to review and endorse the final study report. In cases where a Coordinating Investigator is engaged, the Study Sponsor will select the Coordinating Investigator based upon their experience, qualifications, active study participation, and their willingness and availability to take on this role.

13.5 Regulatory Documentation and Records Retention

The Investigator is required to maintain up-to-date, complete regulatory documentation as indicated by the Study Sponsor and the Investigator's files will be reviewed as part of the ongoing study monitoring. Financial information is to be kept separately.

Additionally, the Investigator must keep study records and source documents consistent with the terms of the clinical study agreement with the Study Sponsor. If the Investigator retires, relocates, or for any other reason withdraws from responsibility of keeping the study records, then the Study Sponsor must be notified and suitable arrangements made for retention of study records and source documents needed to comply with national and international regulations.

13.6 Quality Assurance and Quality Control

The Study Sponsor will secure agreement from all involved parties to ensure direct access to all study related sites, source data and documents, and reports for the purpose of monitoring and auditing by the Study Sponsor, and inspection by domestic and foreign regulatory authorities. Quality control will be applied to each stage of data handling to ensure that all

data are reliable and have been processed correctly. Agreements made by the Study Sponsor with the Investigator/Institution and any other parties involved in the clinical study will be provided in writing as part of the protocol or as a separate agreement.

14 ETHICS

This clinical study must be conducted in accordance with the ethical principles contained within:

- The Declaration of Helsinki, and in compliance with the ICH E6 GCP Consolidated Guideline, ISO 14155:2011, and the applicable US FDA 21 CFR Regulations.
- SOPs of the Study Sponsor and contract research organizations participating in the conduct of the clinical study and all other applicable regulations.
- Notifications and timelines for reporting protocol deviations should be based upon applicable Ethics Committee requirements

The Investigator must ensure that all personnel involved in the conduct of the study are qualified to perform their assigned responsibilities through relevant education, training, and experience. The Investigator and all clinical study staff must conduct the clinical study in compliance with the protocol. Deviations from this protocol, regulatory requirements and/or GCP must be recorded and reported to the Sponsor prior to database lock. If needed, corrective and preventive action should be identified, implemented, and documented within the study records. Use of waivers to deviate from the clinical protocol is prohibited.

Before clinical study initiation, this protocol, the informed consent form, any other written information given to subjects, and any advertisements planned for subject recruitment must be approved by an IRB/IEC. The Investigator must provide documentation of the IRB/IEC approval to the Study Sponsor. The approval must be dated and must identify the applicable protocol, amendments (if any), informed consent form, assent form (if any), all applicable recruiting materials, written information for subject, and subject compensation programs. The IRB/IEC must be provided with a copy of the any periodic safety updates, and all other information as required by local regulation and/or the IRB/IEC. At the end of the study, the Investigator must notify the IRB/IEC about the study's completion. The IRB/IEC also must be notified if the study is terminated prematurely. Finally, the Investigator must report to the IRB/IEC on the progress of the study at intervals stipulated by the IRB/IEC.

Voluntary informed consent must be obtained in writing from every subject and the process shall be documented before any procedure specific to the clinical investigation is applied to the subject. The Investigator must have a defined process for obtaining consent. Specifically,

[figure not shown]
the Investigator, or their delegate, must explain the clinical study to each potential subject and the subject must indicate voluntary consent by signing and dating the approved informed consent form. The subject must be provided an opportunity to ask questions of the Investigator, and if required by local regulation, other qualified personnel. The Investigator must provide the subject with a copy of the consent form written in a language the subject understands. The consent document must meet all applicable local laws and provide subjects with information regarding the purpose, procedures, requirements, and restrictions of the study, along with any known risks and potential benefits associated with the IP and the study, the available compensation, and the established provisions for maintaining confidentiality of personal, protected health information. Subjects will be told about the voluntary nature of participation in the study and must be provided with contact information for the appropriate individuals should questions or concerns arise during the study. The subject also must be told that their records may be accessed by appropriate authorities and Sponsor-designated personnel. The Investigator must keep the original, signed copy of the consent (file in subject's medical records) and must provide a duplicate copy to each subject according to local regulations.

[figure not shown]
The Study Sponsor assures that the key design elements of this protocol will be registered on www.clinicaltrials.gov as required by current regulations and, if applicable, other public databases as required by local country regulations. In addition, results of this study will be made publicly available on www.clinicaltrials.gov regardless of outcome as required by current regulations and, if applicable, in other public databases as required by local country regulations

1.1 Study Objectives

Primary Effectiveness objectives

Primary Effectiveness objectives are to describe the following at Month 3 and Month 6 for all operative eyes:

- Residual manifest cylinder
- IOL rotational stability
- Binocular Best Corrected Distance Visual Acuity (BCDVA) (4 m from spectacle plane) in photopic lighting
- Binocular Distance Corrected Intermediate Visual Acuity (DCIVA) (60 cm from spectacle plane) in photopic lighting
- Binocular Distance Corrected Near Visual Acuity (DCNVA) (40 cm from spectacle plane) in photopic lighting

Safety objectives

Safety objectives are to describe the following at Month 3 and Month 6 for all operative eyes:

- Estimate the cumulative rate of secondary surgical interventions (SSIs)
- Evaluate the rates of severe and most bothersome visual disturbances using the QUVID questionnaire
- Evaluate the rates of adverse events

1.2 Study Description

Key components of the study are summarized in Table 1-1.

Table 1-1 Study Description Summary

Investigational products	ACRYSOF [®] IQ PanOptix [®] Toric Trifocal Intraocular Lenses (IOLs) (Models: TFNT30, TFNT40, TFNT50, TFNT60)
Study Design	Prospective, unmasked, single arm, multi-center, postmarket study; total duration of a subject's participation is approximately 8 months.
Subject population	Adult Asian subjects, 20 years of age or older, who self-identify as being of Chinese, Japanese, Korean, or Mongolian descent, who require bilateral cataract extraction by phacoemulsification and have pre-existing

	
corneal astigmatism, desire an IOL that provides the potential correction for near, intermediate and distance vision, as well as, pre-existing corneal astigmatism.
 
Planned number of subjects enrolled/consented: 63 subjects Planned number of implanted subjects: 56 subjects Planned number of completed subjects: 50 subjects

Number of Sites	Approximately 4-5 sites in Australia
Visits	
Visit 0: Pre-operation Visit 00/00A: Operation Visit 1/1A: Day 1-2 Visit 2/2A: Day 7-14 Visit 3A: Day 30-60 Visit 4A: Day 90-120 Visit 5A: Day 180-210

1.3 Randomization

Not applicable. This is a single arm, unmasked study.

1.4 Masking

This is an open-label study. Treatment assignment may be known to the investigators, subjects or Alcon personnel involved with the planning and execution of the study.

[Redacted]

[Redacted]

[Redacted]

[Redacted]

[Redacted]

[Redacted]

2 Analysis Sets

All subjects will be considered enrolled once they have signed the informed consent form. Subject evaluability will be determined prior to the [Redacted] final database lock, based upon the Deviations and Evaluability Plan (DEP).

2.1 Efficacy Analysis Sets

All-Implanted Analysis Set (AAS) includes all eyes with successful IOL implantation with at least one post-operative visit. The AAS will be the primary analysis set for all effectiveness analyses [REDACTED]

[REDACTED]

- [REDACTED]
- [REDACTED]
- [REDACTED]

[REDACTED]

[REDACTED]

2.2 Safety Analysis Set

The Safety Analysis Set (SS) will include all eyes with attempted IOL implantation (successful or aborted after contact with the eye). The SS will be the primary set for all safety analyses.

3 Subject Characteristics and Study Conduct Summaries

Subject characteristics and study conduct summaries will include tables and listings such as a subject disposition table, demographics (age, sex, race, specific Asian nationality) and baseline characteristics tables (BCDVA, axial length, anterior chamber depth, corneal astigmatism, etc.). Listing of discontinuation, and listing of evaluability and protocol deviations will be provided.

All summary statistics will be based on the type of variable. For categorical variables, such as sex, age group (< 65 years; ≥ 65 years), race and specific Asian nationality, the number and percentage of eyes/subjects in each category for non-missing data will be presented. For continuous variables, the number of non-missing eyes/subjects, mean, standard deviation, median, minimum, and maximum values will be presented.

4 Efficacy Analysis Strategy

4.1 Efficacy Endpoints

All effectiveness endpoints will be summarized as follows for each visit, with Month 3 and 6 visit results being the key endpoint.

Key Endpoints

- Mean monocular residual manifest cylinder for all operative eyes
- Percent of IOLs with < 10 degree rotation for all operative eyes (rotation defined as the difference in IOL axis of orientation from postoperative day 1)
- Mean binocular BCDVA at 4m in photopic lighting condition
- Mean binocular DCIVA at 60cm in photopic lighting condition
- Mean binocular DCNVA at 40 cm in photopic lighting condition

[Redacted text block containing multiple paragraphs of obscured content]

4.2 Efficacy Hypotheses

No formal statistical hypothesis testing is planned for any endpoints. Rather, the data will be summarized using descriptive statistics.

4.3 Statistical Methods for Efficacy Analyses

4.3.1 Analysis of Key Effectiveness Endpoints

4.3.1.1 Residual Manifest Cylinder

Monocular residual manifest cylinder will be summarized by visit for first operative eye, second operative eye and all eyes. The descriptive statistics including the number of eyes, mean, median, standard deviation, minimum, maximum, and two-sided 95% CI of the mean will be presented. Additionally, the number and percent of eyes will be presented for residual manifest cylinder in the following categories: within 0.25 D, within 0.50 D, within 1.00 D and more than 1.00 D.

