6.1 Primary Effectiveness Objective(s)

The following are the Primary Effectiveness objectives and endpoints at Month 3 and Month 6 for all operative eyes:

Table 6-1 Primary Objective(s)

Objective(s)	Endpoint(s)
Residual Manifest Cylinder	Mean monocular residual manifest cylinder for all operative eyes for all IOL models combined
IOL Rotational Stability	Percent of IOLs with <10 degree rotation for all operative eyes (rotation defined as the difference in IOL axis of orientation from postop day 1)
Binocular Best Corrected Distance Visual Acuity (BCDVA) (4 m from spectacle plane) in photopic lighting	Mean binocular BCDVA at 4m in photopic lighting condition
Binocular Distance Corrected Intermediate Visual Acuity (DCIVA) (60 cm from spectacle plane) in photopic lighting	Mean binocular DCIVA at 60cm in photopic lighting condition
Binocular Distance Corrected Near Visual Acuity (DCNVA) (40 cm from spectacle plane) in photopic lighting	Mean binocular DCNVA at 40 cm in photopic lighting condition

[REDACTED]

- [REDACTED]
- [REDACTED]
- [REDACTED]
- [REDACTED]
- [REDACTED]
- [REDACTED]
- [REDACTED]
- [REDACTED]
- [REDACTED]
- [REDACTED]

- [REDACTED]
- [REDACTED]
- [REDACTED]
- [REDACTED]
- [REDACTED]

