4.3.1.2 IOL Rotation

IOL rotation is defined as the difference in IOL axis of orientation from postoperative day 1. IOL rotation will be summarized by sample size, number, percent, and cumulative percent for the following categories of absolute rotation: <5 , <10 , <20 and ≥ 20 degrees. Additionally, descriptive statistics including the number of eyes, mean, median, standard deviation, minimum, maximum, and two-sided 95% CI of the mean will be reported for absolute value of IOL rotation. A listing of eyes with absolute IOL rotation of 10 degrees or more will also be presented.

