4.3.1.3 Binocular Photopic BCDVA, DCIVA and DCNVA

Binocular photopic BCDVA, DCIVA and DCNVA will be summarized as continuous variables with number of subjects, mean, median, standard deviation, minimum, maximum, and two-sided 95% confidence interval for the mean based on Student's *t* statistics, and will be presented at each visit the endpoints are collected. SAS PROC MEANS will be used to generate the confidence interval with option ALPHA=0.05.

For all visual acuity endpoints, the number and percentage of subjects in each of the following visual acuity categories will be presented:

The number and percentage of eyes with visual acuity of

- 0.00 logMAR or better: ≤ 0.00 logMAR

- 0.10 logMAR or better: ≤ 0.10 logMAR
- 0.20 logMAR or better: ≤ 0.20 logMAR
- 0.30 logMAR or better: ≤ 0.30 logMAR
- Worse than 0.30 logMAR: > 0.30 logMAR

[Redacted text block containing multiple lines of blacked-out content]

[REDACTED]

[REDACTED]

[REDACTED]

[REDACTED]

5 Safety Analysis Strategy

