5.3.3 Adverse Events

[figure not shown]
All adverse events (AEs) occurring from when a subject signs informed consent to when a subject exits the study will be accounted for in the reporting. Summary tables for AEs will include the number of affected eyes/subjects, percentage of affected eyes/subjects, 95% two sided confidence intervals, and the number of events. The number and percentage of ocular AEs will be provided for first and second operative eyes and for all eyes. An eye/subject with multiple AEs of the same preferred term will be counted only once toward the total of this preferred term. Listings of AEs will include the lens model, subject ID, Age/Sex, days from surgery, adverse event description, the MedDRA preferred term of the adverse event, and the causality assessment, severity, duration and outcome, when available. Surgery eye and the eye with AE will be provided in the listing of ocular AEs. Adverse events related to the IOL are referred to as adverse device effects (ADE). Listing of pre-treatment AEs, or AEs for non-study eyes will be provided if such cases exist.

Treatment emergent adverse events will be summarized in the following tables and listings:

- Table of All Adverse Events (Serious and Non-Serious Combined)
 - Ocular
 - Non-ocular
- Table of All Adverse Device Effects
 - Ocular
 - Non-ocular
- Table of All Serious Adverse Events (including Serious Adverse Device Effects)
 - Ocular
 - Non-ocular
- Listing of Adverse Event
 - Serious Ocular
 - Serious Non-ocular
 - Non-Serious Ocular
 - Non-Serious Non-ocular

6 Sample Size and Power Calculations

The choice of sample size is not based on statistical considerations.

Approximately 56 subjects will be bilaterally implanted to obtain data for at least 50 subjects (100 eyes) at Month 6, assuming a dropout rate of 10% over a 6 month period. The precision estimates below are presented for individual eye summaries. All eye summaries will have increased precision.

For visual acuity, with a sample size of 50 eyes and assuming a standard deviation of 0.18 logMAR [REDACTED] a two-sided 95%

confidence interval based on large sample z statistics will extend 0.05 logMAR from the observed mean.

[figure not shown]
For residual cylinder, a two-sided 95% confidence interval based on large sample z statistics will extend 0.11 D from the observed mean, assuming a standard deviation of 0.40 D [REDACTED]

[figure not shown]

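### The all-eyes 95% CI for mean residual cylinder has no readable allowance for two eyes per subject; computed per eye, it is too narrow if fellow eyes are positively correlated

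*SAP*

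**What the plan says.** Protocol Table 6-1 lists as its first primary endpoint "Mean monocular residual manifest cylinder for all operative eyes for all IOL models combined", at Month 3 and Month 6. SAP 4.1 repeats it as a key endpoint.

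SAP 4.3.1.1 gives the method: "Monocular residual manifest cylinder will be summarized by visit for first operative eye, second operative eye and all eyes". It continues: "The descriptive statistics including the number of eyes, mean, median, standard deviation, minimum, maximum, and two-sided 95% CI of the mean will be presented". Protocol 12.4.1.2 plans the same statistics "for first eye and second eye and all eyes combined with descriptive statistics". Neither section names a variance method for the all-eyes interval.

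For the binocular acuities, SAP 4.3.1.3 counts people: "summarized as continuous variables with number of subjects, mean, median, standard deviation". It names Student's t and PROC MEANS for those intervals. This is the only confidence interval procedure named in the readable text.

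SAP section 6 expects 50 subjects and 100 eyes at Month 6. It says of its precision figures: "The precision estimates below are presented for individual eye summaries". It then adds: "All eye summaries will have increased precision". It mentions no correlation between fellow eyes.

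**The concern.** Most subjects contribute two eyes to the all-eyes mean. The two eyes share one person, one set of eligibility limits, one toric calculator and the same refraction visits, so their residual cylinders may well be positively correlated. An interval that counts 100 independent eyes would then claim more information than the data hold.

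The per-eye method is a reading of the plan, not a stated rule. It is the default reading because the section lists the interval beside an eye count and an eye-level SD and says nothing about pairing. Running PROC MEANS on eye records would produce exactly this interval.

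The study has no hypothesis test, so its estimates and intervals are its product, and the Protocol (5.2 and 7.2) intends them for health-authority submissions. If the all-eyes interval is computed per eye and fellow eyes are positively correlated, the gain in precision that SAP section 6 announces would be overstated.

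The point does not touch the point estimates, the first-eye and second-eye intervals, the binocular acuity intervals, any percentage, or the stated 0.11 D and 0.05 logMAR.

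**Working it through.** **Inputs.** SD 0.40 D, two-sided 95% and z statistics (SAP section 6, Protocol 12.8). 50 subjects with two eyes each, so 100 eyes (same sections). The between-eye correlation, rho, is not in the documents. It is an assumption, shown from -0.2 to 0.7.

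**Step 1: reproduce the plan's figure.** Single-eye half-width = 1.96 × 0.40 / √50 = 0.1109 D, which rounds to the stated 0.11 D. This uses one eye per subject, so pairing does not affect it.

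**Step 2: per-eye interval for all eyes.** 1.96 × 0.40 / √100 = 0.0784 D. Against the single eye, this looks 1 − 1/√2 = 29% narrower.

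**Step 3: allow for pairing.** With n subjects and two eyes each, Var(mean) = SD²(1 + rho) / (2n). Therefore:

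- correct half-width = 0.0784 × √(1 + rho)
- coverage of the per-eye interval = 2Φ(1.96 / √(1 + rho)) − 1
- true gain over a single eye = 1 − √((1 + rho) / 2)

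| rho | Correct half-width (D) | Coverage of per-eye 95% CI | True gain over a single eye |
|---|---|---|---|
| -0.2 | 0.070 | 97.2% | 37% |
| 0 | 0.078 | 95.0% | 29% |
| 0.1 | 0.082 | 93.8% | 26% |
| 0.3 | 0.089 | 91.4% | 19% |
| 0.5 | 0.096 | 89.0% | 13% |
| 0.7 | 0.102 | 86.7% | 8% |

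For example, at rho 0.5: 0.0784 × √1.5 = 0.0960 D, and 1 − √0.75 = 13%. Over rho 0.1 to 0.7 the half-width falls short by 0.0822 − 0.0784 = 0.004 D up to 0.1022 − 0.0784 = 0.024 D.

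**Step 4: check by simulation.**

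- *Normal data, 50 subjects × 2 eyes, 40,000 runs.* The per-eye t-interval covered 97.2 / 94.9 / 93.7 / 91.7 / 89.0 / 86.6% at rho -0.2 / 0 / 0.1 / 0.3 / 0.5 / 0.7. An interval clustered by subject (49 df) covered 94.8 to 95.2% throughout.
- *45 two-eye and 5 one-eye subjects (95 eyes).* The per-eye interval covered 93.9 / 91.6 / 89.0 / 87.1% at rho 0.1 / 0.3 / 0.5 / 0.7. The clustered interval covered 94.9 to 95.2%.
- *Skewed data (exponential, mean and SD 0.40 D, 20,000 runs), achieved rho 0.26 / 0.45 / 0.66.* The per-eye interval covered 91.3 / 88.4 / 86.0% and the clustered interval 94.1 / 93.7 / 93.6%. Skew costs the clustered interval about one point, so it does not explain the larger loss in the per-eye interval.

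**The case against.** The arithmetic is not in dispute. The case against rests on certainty and importance.

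- **The method is not stated.** An eye count beside the interval does not fix how the variance is computed. The contrast with binocular acuity proves little, because that measure yields one value per subject. This stands: per-eye is the default reading and no more.
- **Redaction.** SAP 4.3.1.1 shows no redaction, but a rule for eye-level data could sit in several blacked-out places: after the binocular sentence in Protocol 12.4, in Protocol 12.4.1.2, or in SAP 2.1, SAP 4.1 or the text after SAP 4.3.1.3. This also stands, and the fix is conditional on it.
- **Nothing is decided by this interval.** The SAP gives no success criterion and plans no test. The endpoint itself is the mean, which is unaffected, and sound single-eye intervals appear in the same summary. This limits the harm. It does not make a 95% label right on an interval that covers 89%.
- **The shortfall is small.** At most 0.024 D over rho 0.1 to 0.7 is about a tenth of the SAP's narrowest cylinder category, 0.25 D. That is true in absolute terms. Relative to the interval, the correct width is 14% greater at rho 0.3 and 22% greater at rho 0.5.
- **The SAP's precision sentence is correct.** All-eye summaries are more precise for any rho below 1, and the SAP states no amount. The 29% in the working follows from the per-eye reading and is not the SAP's claim.

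**Conclusion.** The concern holds and should be fixed. As the plan reads, a primary estimate receives a 95% CI with no allowance for two eyes per subject. If it is computed per eye and fellow eyes are positively correlated, it is too narrow by a factor √(1 + rho): 0.078 D where 0.089 to 0.096 D is needed at rho 0.3 to 0.5, with coverage of 91.4% to 89.0%.

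Three assumptions carry this: the interval is computed per eye, rho is positive, and no redacted rule already deals with pairing. At rho 0 there is no fault, and at negative rho the per-eye interval is too wide.

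The same probably applies to the interval for mean rotation in SAP 4.3.1.2: "two-sided 95% CI of the mean will be reported for absolute value of IOL rotation". That is a supporting summary counted in eyes. Its section states no split by eye, so the point holds there only if both eyes are pooled.

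**What to change.** If a redacted section already covers pairing, the sponsor need only confirm it. Otherwise, add one sentence to SAP 4.3.1.1, and to 4.3.1.2 for any interval that pools both eyes:

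> The 95% CI of the mean for all eyes will use a variance clustered by subject, with t on (number of subjects − 1) degrees of freedom.

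PROC SURVEYMEANS with subject as the CLUSTER variable does this. It leaves the eye-level mean unchanged and accommodates subjects with one eye. With complete pairs it equals a t-interval on subject means, so the two are interchangeable there. The first-eye and second-eye intervals stay as planned.

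The cost is one or two sentences and a change of procedure, with no new data. If rho is 0, the interval widens by about 1% (t factor 2.010 on 49 df against 1.984 on 99 df). In large-sample terms it widens by about 5 / 14 / 22 / 30% at rho 0.1 / 0.3 / 0.5 / 0.7, which is the width it should have.
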